5.5.2. Withdrawal Procedures

In the event that the decision is made to permanently discontinue the study drug, the subject will be withdrawn from the study and the EOT visit should be conducted. Reasonable efforts should be made to have the subject return for the safety follow-up visit (see Section 6.4). The last date of the last dose of study drug and the reason for subject withdrawal will be recorded in the eCRF.

If a subject is withdrawn from all study treatment:

- The study monitor or sponsor must be notified.
- The reason(s) for withdrawal must be documented in the subject's medical record and in the eCRF.

Note: The reason for withdrawal from treatment may be different than the reason for withdrawal from study.

- The EOT visit should be performed.
- The date of the EOT visit should be recorded in the eCRF and IRT.
- Subjects must be followed for safety until the time of the follow-up visit or until study drug–related toxicities resolve, return to baseline, or are deemed irreversible, or until the subject begins new anticancer therapy, whichever is longest.

If the subject discontinues study treatment and actively withdraws consent for collection of follow-up data (safety follow-up), then no additional data collection should occur; however, subjects will have the option of withdrawing consent for study treatment but continuing in the safety follow-up period.

5.6. Concomitant Medications

Medications or vaccinations specifically prohibited in the exclusion criteria are not allowed during the study. If there is a clinical indication for one of these or other medications, discontinuation from study therapy may be required. The investigator should discuss any questions regarding this with the sponsor. The final decision on any supportive therapy rests with the investigator and/or the subject's primary physician. However, the decision to continue the subject on study therapy requires the mutual agreement of the investigator, the sponsor, and the subject.

All concomitant medications received within 28 days before the first dose of study treatment and 30 days after the last dose of study treatment should be recorded. Concomitant medications administered in the 30 days after the last dose of study treatment should be recorded for SAEs and AEs as defined in Section 8.

5.6.1. Permitted Medications

All treatments that the investigator considers necessary for a subject's welfare may be administered at the discretion of the investigator in keeping with the community standards of medical care. All concomitant medication will be recorded on the eCRF, including all prescription, over-the-counter, herbal supplements, and IV medications and fluids. If changes occur during the study period, documentation of drug regimen, frequency, route, and date may also be included on the eCRF.

5.6.2. Restricted Medications

- Systemic steroids may be used at doses ≤ 10 mg/day prednisone or equivalents.
- Use of coumarin-based anticoagulants is discouraged. Low-dose warfarin (1 mg) is acceptable; however, doses that increase the INR are discouraged and will require dose modification. If an alternative to coumarin-based anticoagulants cannot be used, dose modifications of the warfarin may be needed. Based on the observed magnitude of epacadostat/warfarin PK interaction and PK/pharmacodynamic modeling results, for an epacadostat dose of 300 mg BID, the dose of warfarin should be reduced by approximately one-third after initiation of epacadostat administration based on approximately 30% to 40% reduction in S- and R-warfarin oral clearance values. Close INR monitoring is recommended for subjects on a stable dose of warfarin who are starting treatment with epacadostat. Based on PK/pharmacodynamic modeling, recommendations for warfarin dose modifications for subjects receiving other epacadostat doses are summarized in [Table 20](#) based on the INR before starting epacadostat.

Table 20: Recommendations for Warfarin Dose Modifications

Stable Baseline INR	Epacadostat Dose		
	≤ 100 mg BID	200 mg BID	300 mg BID
INR ≤ 2.5	Close INR monitoring	Close INR monitoring	Reduce warfarin by ~33% and monitor INR
INR > 2.5	Close INR monitoring	Reduce warfarin by 20%-25% and monitor INR	Reduce warfarin by ~33% and monitor INR

- Use of the anticonvulsant carbamazepine (a UGT1A9 inducer) is prohibited; an alternative to carbamazepine should be used, if possible.

5.6.3. Prohibited Medications

Subjects are prohibited from receiving the following therapies starting from screening through EOT period of this study unless otherwise noted below:

- Any investigational medication other than the study drugs.
- Any anticancer medications, including chemotherapy or biologic therapy other than the study medications.
- Any chronic immunosuppressive treatment for any reason. (**Note:** Inhaled or topical steroids are allowed, and systemic steroids at doses ≤ 10 mg/day of prednisone or equivalents are allowed, as described in Section 5.6.2, and immune suppressants are allowed for short-term treatment for immune toxicities or as prophylaxis for contrast allergy for imaging procedures.)
- Radiation therapy.

Note: In the presence of a mixed response (some lesions improving or stable and other lesions progressing), radiation therapy to a symptomatic solitary lesion or to the brain is allowed.

- Administration of a live attenuated vaccine within 30 days before the first dose of study treatment and while participating in the study. Examples of live vaccines include, but are not limited to, the following: measles, mumps, rubella, chicken pox, yellow fever, rabies, BCG, and typhoid vaccine. Seasonal influenza vaccines for injection are generally killed virus vaccines and are allowed; however, intranasal influenza vaccines are live attenuated vaccines and are not allowed.
- Any MAOI or drug associated with significant MAOI activity agents is prohibited from 21 days before Day 1 through 2 weeks after the final dose of epacadostat has been administered (see [Appendix D](#)).
- Any immunologic-based treatment for any reason from screening through follow-up visit is prohibited.

Note: Completed adjuvant therapy (eg, vaccines) with medical monitor approval, inhaled or topical steroids, and systemic steroids at doses ≤ 10 mg/day prednisone equivalents are allowed, as described in Section [5.6.2](#).

- Any UGT1A9 inhibitor or inducer, including aceclofenac, acitretin, amitriptyline, androsterone, carbamazepine, cyclosporine, dasatinib, diclofenac, diflunisal, efavirenz, erlotinib, estradiol (17-beta), flutamide, gefitinib, gemfibrozil, glycyrrhetic acid, glycyrrhizin, imatinib, imipramine, ketoconazole, lamotrigine, linoleic acid supplements, mefenamic acid, mycophenolic acid, niflumic acid, nilotinib, oxcarbazepine, phenobarbital, phenylbutazone, phenytoin, probenecid, propofol, quinidine, rifampin, ritonavir, sorafenib, sulfinpyrazone, valproic acid, and verapamil.

Note: Propofol, when used for short-term sedation during surgical/biopsy procedures, is allowed after consultation with the medical monitor. The epacadostat dose may be taken on the morning of the procedure, and the evening dose held following the procedure. Epacadostat may be resumed the next day.

Subjects who, in the assessment by the investigator, require the use of any of the aforementioned treatments for clinical management should be removed from the study. Subjects may receive other medications that the investigator deems to be medically necessary.

The exclusion criteria (Section [3.2](#)) describe other medications that are prohibited during this study. There are no prohibited therapies during the post-treatment follow-up period.

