Lirilumab will be administered as a 240 mg IV infusion over 60 minutes (\pm 5 minutes) on Day 1 of Cycle 1 and then Day 1 of every other cycle thereafter (ie, Cycle 3, Cycle 5, etc). Lirilumab will be administered after nivolumab on visit days when both agents are given. Intrasubject dose escalation of lirilumab is not allowed.

Treatment Cycles and Duration of Treatment:

Study treatment will be administered in continuous 14-day cycles. Subjects will continue to receive study treatment for up to 2 years as long as the subject is deriving benefit and has not met any of the Protocol-defined conditions for treatment discontinuation. Intrasubject dose-escalation is not permitted.

Study Schedule/Procedures:

The study comprises the following parts:

- **Screening:** Up to 28 days before enrollment. Screening will begin at the time that the subject signs the informed consent and will continue until the date the subject is enrolled in the study (Cycle 1 Day 1).
- **Treatment:** Treatment cycles will be 14 days in length. Subjects will have regularly scheduled study visits on Day 1 (± 3 days) of each cycle. Clinic visits will also occur on Day 8 (± 1 day) during the first 3 cycles.
- **End of treatment:** + 7 days after withdrawal from study treatment.
- **Safety follow-up:** 30 days (+ 7 days), 100 days (± 7 days), and 150 days (± 7 days; Treatment Group B only) after the last dose of study treatment.

Safety Assessments:

Subjects will have regularly scheduled study visits at the clinical site on Day 1 of every cycle where targeted physical examinations, vital sign collection, collection of concomitant medications, and AE assessments will be performed. Twelve-lead ECGs will be performed at screening, Cycle 1 Day 1, Cycle 2 Day 1, and at the end-of-treatment visit. Laboratory assessments will be collected during each treatment cycle. Toxicities will be monitored continuously and will be graded using the National Cancer Institute's CTCAE v4.03 criteria.

Regular telephone conferences with study investigators will be scheduled by the sponsor in order to review cohort-specific data and overall safety data, agree on dose escalation, adjudicate individual high-grade AEs as potentially dose-limiting, and guide other major study decisions.

Efficacy Assessments:

Disease assessments will be performed based on RECIST v1.1 [REDACTED]

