4.4. Duration of Treatment and Subject Participation

After signing the ICF, screening assessments may be completed over a period of up to 28 days. Each subject enrolled in the study may continue to receive study treatment in continuous 14-day cycles for up to 2 years, as long as they are deriving benefit and have not met any of the Protocol-defined conditions for treatment withdrawal (see Section 5.5.1). If the subject discontinues study treatment, the treatment period will end and the subject will enter the safety follow-up period (see Section 6.4). Study participation, including post-treatment safety follow-up, is expected to average approximately 12 to 18 months per individual subject.

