5.4.6. Procedure for Subjects Exhibiting Serotonin Syndrome

As noted in Section 1.2.1, there is a risk that epacadostat may cause an increase in serotonin levels in the brain that might trigger SS (Boyer and Shannon 2005) when administered in combination with other serotonergic agents. This syndrome has been most closely associated with use of MAOIs, meperidine, linezolid, or methylene blue; all of these agents are prohibited during the study. Selective serotonin reuptake inhibitors and SNRIs are permitted in the study. Serotonin syndrome usually manifests with autonomic changes, mental status changes, and neurological findings. These mild, moderate, and severe signs and symptoms of SS (summarized in Table 17) should be evaluated in the context of possible comorbid conditions as well.

The following procedures will be implemented if subjects exhibit the signs/symptoms of SS described in Table 17, including tremor; hyperreflexia; and spontaneous, ocular, or inducible clonus, together with agitation, fever, diaphoresis, or muscle rigidity:

- Immediately interrupt all treatment administration.
- Immediately interrupt any SSRI or SNRI administration.
- Provide appropriate medical management of the subject until all signs/symptoms are resolved (eg, IV fluids and/or sympathomimetic amines for hypotension, benzodiazepines for agitation, administration of 5-hydroxytryptamine antagonists, such as cyproheptadine).
- If etiologies other than SS are excluded, nivolumab and ipilimumab administration may be resumed unless other AE management guidelines apply for the specific event.
- If subject chooses to withdraw from the study or must restart treatment with SSRI or SNRI, the subject should be scheduled for a follow-up visit. Treatment with SSRI or SNRI may be initiated 2 weeks after resolution of signs and symptoms of SS.
- If a subject had experienced moderate or severe unconfounded SS in the opinion of the investigator, without concomitant SSRI or SNRI use, or serotonergic concomitant medications, only nivolumab/ipilimumab administration may be resumed; epacadostat treatment should be permanently discontinued.

Table 17: Sign and Symptoms of Serotonin Syndrome

Seriousness	Autonomic Signs	Neurological Signs	Mental Status	Other
Mild	Afebrile or low-grade fever Tachycardia Mydriasis Diaphoresis or shivering	Intermittent tremor Akathisia Myoclonus Mild hyperreflexia	Restlessness Anxiety	

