6.4. Follow-Up

6.4.1. Safety Follow-Up

The safety follow-up period is the interval between the EOT visit and the scheduled follow-up visits, which should occur approximately 30 days (+ 7 days), 100 days (\pm 7 days), and 150 days

(± 7 days; Treatment Group B only) after the EOT visit (or after the last dose of study treatment if the EOT visit was not performed). Adverse events and SAEs must be reported up until at least 100 days after the last dose of study treatment for Treatment Group A, up until at least 150 days after the last dose of study treatment for Treatment Group B, or until toxicities resolve, return to baseline, or are deemed irreversible, whichever is longer. Reasonable efforts should be made to have the subject return for the follow-up visits and to report any AEs that may occur during this period. If a subject is scheduled to begin a new anticancer therapy before the end of the safety follow-up period, the applicable safety follow-up visit should be performed before new anticancer therapy is started. After the safety follow-up period, there will be no additional assessments and the study will be considered complete.

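### The closing sentence of 5.6.3 lifts all drug prohibitions in follow-up and so contradicts the MAOI rule in the same section, by 7 to 14 days for a subject whose last epacadostat dose coincides with withdrawal

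*Combined protocol and SAP*

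**What the plan says.** Section 5.6.3 lists therapies that are barred "starting from screening through EOT period of this study unless otherwise noted below". One of the bullets does note otherwise. Use of an MAOI, or of a drug with significant MAOI activity, "is prohibited from 21 days before Day 1 through 2 weeks after the final dose of epacadostat has been administered". The section closes with: "There are no prohibited therapies during the post-treatment follow-up period".

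Three other places set the timing. Section 6.4.1 defines the period: "The safety follow-up period is the interval between the EOT visit and the scheduled follow-up visits". The synopsis places the EOT visit at plus "7 days after withdrawal from study treatment", and Table 21 gives the same + 7 day window. Section 4.4 says: "If the subject discontinues study treatment, the treatment period will end and the subject will enter the safety follow-up period", and points to Section 6.4 for that period.

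The reason for the ban is in Section 5.4.6. It links serotonin syndrome most closely to MAOIs, meperidine, linezolid and methylene blue, and adds that "all of these agents are prohibited during the study".

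**The concern.** The MAOI bullet has its own end date, tied to the last epacadostat dose. The closing sentence removes every prohibition once follow-up begins. For any day that is both in follow-up and within 2 weeks of the last epacadostat dose, the two statements cannot both be followed. Both are current text in one section, and nothing in the protocol says which prevails.

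What is at stake is conduct and subject safety. A site that relies on the closing sentence could start linezolid, for example, while the protocol's own washout is still running. The precaution would then end before the date the sponsor set for it.

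**Working it through.** The check is calendar arithmetic. The plan states no figure for the overlap, so there is none to reproduce.

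Inputs:
- Length of the MAOI ban after the last epacadostat dose: 2 weeks = 14 days (5.6.3).
- Start of follow-up: the EOT visit (6.4.1).
- Timing of the EOT visit: 0 to 7 days after withdrawal from study treatment (synopsis and Table 21, reading + 7 days as a one-sided window).
- First safety follow-up visit: 30 days (+ 7 days). The ban expires on day 14, before that visit, so all of the overlap lies inside follow-up.

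Formula: let *d* be the number of days from the last epacadostat dose to the start of follow-up. Then days of conflict = max(0, 14 − *d*).

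Last epacadostat dose coincides with withdrawal, so *d* is the delay to the EOT visit:
- EOT visit on day 0: 14 − 0 = 14 days.
- EOT visit on day 3: 14 − 3 = 11 days.
- EOT visit on day 7: 14 − 7 = 7 days.

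Epacadostat stopped earlier than the other drugs:
- Stopped 7 days before withdrawal: *d* runs from 7 to 14, giving 7 to 0 days.
- Stopped 10 days before follow-up begins: 14 − 10 = 4 days.
- Stopped 14 or more days before follow-up begins: 0 days.

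The earlier-stop cases can occur. Section 5.2.1 lets subjects still on treatment at Amendment 2 stop epacadostat at the investigator's discretion. Section 5.4.4 allows all study drugs to be held for up to 28 days for toxicity, and a subject withdrawn late in such a hold would have no overlap.

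**The case against.** The strongest reply is that the documents already point to one answer. The lead-in of 5.6.3 allows bullets to set their own end dates. An end date counted from the last epacadostat dose makes sense only if it can run past EOT. Section 5.4.6 calls these agents prohibited for the duration of the study, and under 6.5 a subject can complete the study by finishing safety follow-up. Section 5.6 disallows during the study any medication barred by the exclusion criteria, which reaches MAOIs through exclusion 21, and it sends questions to the sponsor. All of this stands as evidence of intent, and it is why the point is minor. It does not remove the conflict. The lead-in qualifies the default window, whereas the closing sentence speaks directly about the period after it, and no rule ranks the specific bullet above the general sentence.

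A reader might infer that the protocol has two competing starts for follow-up, so that the conflict is always 14 days. The documents do not support that. Section 4.4 refers to Section 6.4 for the period, so it need not be a second definition. The parenthesis in 6.4.1, "or after the last dose of study treatment if the EOT visit was not performed", says when the follow-up visits are timed from, not when the period starts. The 14-day upper end needs neither reading, because a day-0 EOT visit gives it.

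A reader might also want every bullet that reaches into follow-up restored. The immunologic-treatment bullet, the live-vaccine bullet and exclusion 22 on UGT1A9 agents also sit badly with the closing sentence. For these the documents do not show which text the sponsor means to govern, and extending a restriction on post-treatment care is a clinical decision.

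**Conclusion.** The contradiction is real and minor. It amounts to 7 to 14 days of the 14-day MAOI window, on two assumptions: the last epacadostat dose coincides with withdrawal, and the EOT visit falls 0 to 7 days later. It shrinks as epacadostat stops earlier, and it is zero once the gap to follow-up reaches 14 days.

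A reader might infer a material safety gap. The documents do not support that. The rat data in 1.2.1 suggest that serotonin syndrome is unlikely even with MAOIs such as linezolid. Enrollment is closed, no subject entered Treatment Group B, and ongoing Group A subjects may stop epacadostat. The number of Group A subjects still taking it is not given, so the number exposed to the conflicting text cannot be stated.

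No endpoint, analysis population, alpha level or power figure is affected.

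**What to change.** Keep the closing sentence of 5.6.3 and add an exception, so that it reads: "There are no prohibited therapies during the post-treatment follow-up period", *except that MAOIs and drugs with significant MAOI activity stay prohibited until 2 weeks after the last epacadostat dose*. This takes the MAOI conflict from 7 to 14 days down to 0.

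The cost is one sentence of protocol wording, with no change to data collection or analysis. The sponsor should decide separately which text governs the immunologic-treatment, live-vaccine and UGT1A9 provisions in follow-up. Those decisions are not part of this change.

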6. STUDY ASSESSMENTS

All study assessments will be performed as indicated in the schedule of clinical assessments ([Table 21](#) and [Table 23](#)), and all laboratory assessments will be performed as indicated in [Table 22](#) and [Table 24](#). [Table 25](#) presents a summary of local clinical laboratory analytes to be assessed. The order of assessments is suggested by the order of mention within the schedule. See Section [7](#) for instructions on each assessment. Further details of study procedures and assessments can be found in the Study Reference Manual.

Table 21: Schedule of Clinical Assessments – Treatment Group A (Epacadostat + Nivolumab + Ipilimumab)

Visit	Screening	Treatment Period (14-Day Cycles)				EOT	Safety Follow-Up ^b		Comments
		Cycles 1 Through 3		Cycle 4 and Beyond	Disease Status ^a		30 Days After EOT	100 Days After EOT	
		Day 1	Day 8	Day 1	See Footnote a		+ 7 Days	+ 7 Days	
Evaluation/Window	Days -28 to -1	± 3 Days	± 1 Day	± 3 Days	± 7 Days	+ 7 Days	+ 7 Days	± 7 Days	
Administrative Procedures									
Informed consent	X								
Contact IRT	X	X		X		X			
Inclusion/exclusion criteria	X	X							
Prior medical and cancer history	X								
Prior and concomitant medications	X	X	X	X		X	X	X	
Reminder card		X	X	X		X	X		
Clinical Procedures/Assessments									
Comprehensive physical examination and height	X								
Targeted physical examination		X	X ^b	X		X	X	X	
Vital signs and weight	X	X	X	X		X	X	X	
ECOG performance status	X								
Laboratory assessments	X	X	X	X		X	X		See Table 22 for required laboratory assessments.
12-Lead ECG	X	X*				X			* Cycle 1 Day 1 and Cycle 2 Day 1. See Section 7.5.4 for details.
AE assessment	X	X	X	X		X	X	X	
Tumor tissue collection	X								Only Phase 1 subjects. See Table 22 for Phase 2 fresh biopsy collection timepoints.

Table 21: Schedule of Clinical Assessments – Treatment Group A (Epcadostat + Nivolumab + Ipilimumab) (Continued)

Visit	Screening	Treatment Period (14-Day Cycles)				EOT	Safety Follow-Up ^b		Comments
		Cycles 1 Through 3		Cycle 4 and Beyond	Disease Status ^a		30 Days After EOT	100 Days After EOT	
		Day 1	Day 8	Day 1	Q8W		+ 7 Days	+ 7 Days	
Evaluation/Window	Days -28 to -1	± 3 Days	± 1 Day	± 3 Days	± 7 Days	+ 7 Days	+ 7 Days	± 7 Days	
Study Drug Administration									
Administer epacadostat in clinic		X	X						█ Epacadostat should be administered before nivolumab and ipilimumab.
Administer nivolumab		X		X					Nivolumab should be administered before ipilimumab at applicable visits.
Administer ipilimumab		X		X					Ipilimumab will be administered on Cycle 1 Day 1 and then on Day 1 of every 3rd cycle (Cycles 4, 7, 10, etc).
Efficacy Assessments									
Radiologic tumor assessments	X				X				The same imaging technique should be used in a subject throughout the study. If imaging shows PD, an imaging assessment should be performed at a minimum of 4 weeks and maximum of 8 weeks later to confirm PD █ See Section 7.6 for complete details on imaging requirements.

^a On-study imaging will be performed at 8 and 16 weeks (± 7 days) after the start of treatment and then every 12 weeks (± 7 days) thereafter until the end of study treatment. Imaging should follow calendar days starting with Day 1 of study treatment and should NOT be adjusted for delays in cycle starts.

^b The mandatory safety follow-up visits should be conducted approximately 30 and 100 days after the last dose of study treatment or before the initiation of a new anticancer treatment, whichever comes first.

^c Only required for Day 8 visits if there are ongoing AEs > Grade 2.

Table 22: Schedule of Laboratory Assessments – Treatment Group A (Epacadostat + Nivolumab + Ipilimumab)

Visit	Screening	Treatment Period (14-Day Cycles)			EOT	Follow-Up	Comments
		Cycles 1 Through 3		Cycle 4 and Beyond		30 Days After EOT	
		Day 1	Day 8	Day 1			
Evaluation/Window	Days -28 to -1	± 3 Days	± 1 Day	± 3 Days	+ 7 Days	+ 7 Days	
Local Laboratory Tests^a							
Serum chemistry	X	X	X	X	X	X	Additional assessment of serum chemistry as clinically indicated.
Hematology with differential	X	X		X	X	X	Additional assessment of hematology as clinically indicated.
Liver chemistry tests	X	X	X	X	X	X	If baseline liver chemistry tests are WNL and increase to ≥ Grade 1, testing should be performed twice weekly until resolved to baseline. If baseline liver chemistry tests were Grade 1 at baseline and increase to ≥ Grade 2, twice weekly testing should be performed until resolved to ≤ Grade 1.
Coagulation panel	X			X	X		Screening, Cycle 4, and every 3rd cycle thereafter.
Endocrine function tests	X			X	X	X	Screening, Cycle 4, and every 3rd cycle thereafter.
Urinalysis	X				X		
Hepatitis B and C	X						
Serum pregnancy test ^b (childbearing females only)	X				X		Required for all women of childbearing potential during screening; must be within 72 hours before the first dose of study treatment.

^a All safety laboratory assessments will be performed locally.

^b Urine pregnancy tests may be conducted at additional time points as medically indicated.

Table 23: Schedule of Clinical Assessments – Treatment Group B (Epacadostat + Nivolumab + Lirilumab)

Visit	Screening	Treatment Period (14-Day Cycles)				EOT	Follow-Up					Comments	
		Cycles 1 Through 3		Cycle 4 and Beyond	Disease Status ^a		Safety ^b			Disease Status ^c	Survival		
		Day 1	Day 8	Day 1	Q8W		30 Days After EOT	100 Days After EOT	150 Days After EOT	Q8W	Q12W		
Evaluation/Window	Days -28 to -1	± 3 Days	± 1 Day	± 3 Days	± 7 Days	+ 7 days	+ 7 Days	± 7 Days	± 7 Days	± 7 Days	± 7 Days	± 7 Days	
Administrative Procedures													
Informed consent	X												
Contact IRT	X	X		X		X							
Inclusion/exclusion criteria	X	X											
Prior medical and cancer history	X												
Prior and concomitant medications	X	X	X	X		X	X	X	X				
Reminder card		X	X	X		X	X	X					
Poststudy anticancer therapy status							X	X	X	X	X		
Survival status												X	
Clinical Procedures/Assessments													
Comprehensive physical examination and height	X												
Targeted physical examination		X	X ^d	X		X	X	X	X				Only required for Day 8 visits if there are ongoing AEs > Grade 2.
Vital signs and weight	X	X	X	X		X	X	X	X				
ECOG performance status	X	X		X			X	X	X				
Laboratory assessments	X	X	X	X		X	X						See Table 22 for required laboratory assessments.
HPV status	X												Subjects with SCCHN (oropharyngeal only) must have documentation of HPV status (eg, p16 expression).
12-Lead ECG	X	X*				X							* Cycle 1 Day 1 and Cycle 2 Day 1. See Section 7.5.4 for details.
AE assessment	X	X	X	X		X	X	X	X				
Tumor tissue collection	X												Only Phase 1 subjects. See Table 24 for Phase 2 fresh biopsy collection timepoints.

Table 23: Schedule of Clinical Assessments – Treatment Group B (Epacadostat + Nivolumab + Lirilumab) (Continued)

Visit	Screening	Treatment Period (14-Day Cycles)				EOT	Follow-Up					Comments
		Cycles 1 Through 3		Cycle 4 and Beyond	Disease Status ^a		Safety ^b			Disease Status ^c	Survival	
		Day 1	Day 8	Day 1	Q8W		30 Days After EOT	100 Days After EOT	150 Days After EOT	Q8W	Q12W	
Evaluation/Window	Days -28 to -1	± 3 Days	± 1 Day	± 3 Days	± 7 Days	+ 7 days	+ 7 Days	± 7 Days	± 7 Days	± 7 Days	± 7 Days	
Study Drug Administration												
Administer epacadostat in clinic		X	X									Epacadostat will be administered in the clinic for visits [REDACTED] (Cycle 1 Day 1, Cycle 1 Day 8, Cycle 2 Day 1). Epacadostat should be administered before nivolumab and lirilumab.
Administer nivolumab		X		X								Nivolumab should be administered before lirilumab at applicable visits.
Administer lirilumab		X		X								Lirilumab will be administered on Cycle 1 Day 1 and then Day 1 of every other cycle (Cycles 3, 5, 7, etc).
Efficacy Assessments												
Radiologic tumor assessments	X				X						X	The same imaging technique should be used in a subject throughout the study. If imaging shows PD, an imaging assessment should be performed at a minimum of 4 weeks and maximum of 8 weeks later to confirm PD [REDACTED]. See Section 7.6 for complete details on imaging requirements.

^a On-study imaging will be performed every 8 weeks (± 7 days) for the first 12 months and then every 12 weeks (± 7 days) thereafter. Imaging should follow calendar days starting with Day 1 of study treatment and should NOT be adjusted for delays in cycle starts.

^b The mandatory safety follow-up visits should be conducted approximately 30, 100, and 150 days after the last dose of study treatment or before initiation of a new anticancer treatment, whichever comes first.

^c For subjects who discontinue treatment for reasons other than disease progression, every effort should be made to continue monitoring their disease status every 8 weeks (± 7 days) for the first 12 months after the start of treatment and then every 12 weeks (± 7 days) thereafter by radiographic imaging until 1) start of new anticancer therapy, 2) confirmed disease progression, 3) death, 4) the end of the study, or 5) withdrawal of consent, whichever occurs first.

^d Only required for Day 8 visits if there are ongoing AEs > Grade 2.

Table 24: Schedule of Laboratory Assessments – Treatment Group B (Epacadostat + Nivolumab + Lirilumab)

Visit	Screening	Treatment Period (14-Day Cycles)			EOT	Follow-Up	Comments
		Cycles 1 Through 3		Cycle 4 and Beyond		30 Days After EOT	
		Day 1	Day 8	Day 1			
Evaluation/Window	Days -28 to -1	± 3 Days	± 1 Day	± 3 Days	+ 7 Days	± 7 Days	
Local Laboratory Tests^a							
Serum chemistry	X	X	X	X	X	X	Additional assessment of serum chemistry as clinically indicated.
Hematology with differential	X	X		X	X	X	Additional assessment of hematology as clinically indicated.
Liver chemistry tests	X	X	X	X	X	X	If baseline liver chemistry tests are WNL and increase to ≥ Grade 1, testing should be performed twice weekly until resolved to baseline. If baseline liver chemistry tests were Grade 1 at baseline and increase to ≥ Grade 2, twice weekly testing should be performed until resolved to ≤ Grade 1.
Coagulation panel	X			X	X		Screening, Cycle 4, and every 3rd cycle thereafter.
Endocrine function tests	X			X	X	X	Screening, Cycle 4, and every 3rd cycle thereafter.
Urinalysis	X				X		
Hepatitis B and C	X						
Serum pregnancy test ^b (childbearing females only)	X				X		Required for all women of childbearing potential during screening and must be within 72 hours before the first dose of study treatment.

**Table 24: Schedule of Laboratory Assessments – Treatment Group B (Epacadostat + Nivolumab + Lirilumab)
 (Continued)**

Visit	Screening	Treatment Period (14-Day Cycles)			EOT	Follow-Up	Comments
		Cycles 1 Through 3		Cycle 4 and Beyond		30 Days After EOT	
		Day 1	Day 8	Day 1			
Evaluation/Window	Days -28 to -1	± 3 Days	± 1 Day	± 3 Days	+ 7 Days	± 7 Days	

^a All safety laboratory assessments will be performed locally.

^b Urine pregnancy tests may be conducted at additional time points as medically indicated.

Table 25: Local Laboratory Tests: Required Analytes

Serum Chemistries	Hematology	Urinalysis	Hepatitis Screening	Endocrine Function Tests
Albumin Bicarbonate Blood urea nitrogen Calcium Chloride Creatinine Glucose Lactate dehydrogenase Phosphate Potassium Sodium Total protein Uric acid Amylase Lipase	Complete blood count, including: 
 • Hemoglobin • Hematocrit • Platelet count • Red blood cell count • White blood cell count Differential count, including: 
 • Basophils • Eosinophils • Lymphocytes • Monocytes • Neutrophils Absolute values must be provided for: 
 • Lymphocytes • Neutrophils 	Color and appearance pH and specific gravity Bilirubin Glucose Ketones Leukocytes Nitrite Occult blood Protein	Hepatitis B surface antigen HBV-DNA HCV-RNA or HCV antibody where is HCV RNA is not SOC	Adrenocorticotrophic hormone Serum cortisol (9 AM) ^a Luteinizing hormone ^b Prolactin TSH Free thyroxine (T4) Total triiodothyronine (T3) Serum testosterone (9AM) ^{a,b}
Liver Chemistry Tests			Pregnancy Testing	Coagulation
Alkaline phosphatase ALT AST Total bilirubin Direct bilirubin (if total bilirubin is elevated above ULN)			Female subjects of childbearing potential only require a serum test at screening. Pregnancy tests (serum or urine) should be repeated if required by local regulations.	PT or INR aPTT or PTT

^a Serum cortisol and testosterone ideally should be drawn close to 9 AM but can be performed any time before 12 PM.

^b Not needed in women, surgically castrated men, or men taking LH-releasing hormone agonist therapy.

